**Treatment of Mild/Moderate Bleeding Episodes:**

Treatment of a mild/moderate bleeding episode will be initiated as soon as possible, but certainly within 4 hours of first symptoms of the onset of the bleeding episode. Treatment will consist of IV administration of either 75  $\mu\text{g}/\text{kg}$  or 225  $\mu\text{g}/\text{kg}$  (depending on randomization) of LR769 as a bolus injection administered in  $\leq2$  minutes.

During the 75  $\mu\text{g}/\text{kg}$  treatment regimen, the initial 75  $\mu\text{g}/\text{kg}$  dose may be followed 3 hours  $\pm 15$  minutes later with 75  $\mu\text{g}/\text{kg}$  every 3 hours  $\pm 15$  minutes until the bleed is successfully treated. A maximum of 8 administrations in total over a 21-hour period are allowed in this

treatment regimen for mild/moderate bleeding episodes.

During the 225 µg/kg treatment regimen, the initial 225 µg/kg treatment may be followed 9 hours ± 15 minutes later with 75 µg/kg every 3 hours ± 15 minutes until the bleed is successfully treated. A maximum of 6 administrations in total within a 21-hour period are allowed in this treatment regimen for mild/ moderate bleeding episodes.

If the bleeding episode is not successfully treated as assessed as an excellent or good response at 24 hours after the first administration, treatment with LR769 may not be continued and alternative treatment must be considered depending on the remaining symptoms (and be noted as concomitant medication). Treatment of this bleeding episode should not be continued with LR769 (study drug) in that case. The patient's physician may determine the best treatment in that case. This may be another bypassing agent [REDACTED]  
[REDACTED] or other hemostatic treatment.

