### **Duration of Treatment:**

In Phase A, patients will receive a single administration of study drug in a non-bleeding state. Patients are eligible for treatment of a bleeding episode 24 hours after the initial administration of LR769 in Phase A. Treatment for such bleeding episodes will continue until satisfactory resolution of the bleeding episode has occurred, but with a last administration of study drug no later than 21 hours after first treatment (with an efficacy assessment at 24 hours after initiation of treatment). Severe bleeding episodes may need to be treated for several days until the investigator determines the bleeding has stopped and the risk of recurrence of the bleeding is minimal.

Patients will be followed initially at 3 weeks  $\pm$ 2 days, and 6 weeks  $\pm$ 5 days following the first

administration in Phase A and subsequently every 6 weeks  $\pm$  5 days. Patients may be treated for multiple bleeding episodes during the course of the study. All patients will be followed for at least 6 months after the first LR769 administration, or, in case the study ends, for 14 days ( $\pm$ 2 days) after the last administration of study drug.

The study will continue until at least 352 mild/moderate bleeding episodes have been treated and at least 6 months have passed since first administration of LR769 in at least 22 patients (approximately 11 from each age group).

The overall duration of the study is approximately 16 months from First Patient First Visit until Last Patient Last Visit. The enrollment period is expected to last approximately 9 months.

The duration of an individual patient's participation in this part of the study (from signing the informed consent form until the last study visit in Phase B) may vary from approximately 7 months to approximately 16 months depending on when the patient is enrolled, unless discontinued prematurely.

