The null hypothesis will be tested using a one-sided, one-sample, normal approximation test and a test statistic obtained by dividing ( $\hat{p} - 0.55$ ) by its estimated standard error, taking into account the correlation between bleeding episodes for a given patient. The test will be conducted at the 0.0125 level (adjusted from 0.025 to 0.0125 to account for multiplicity of testing). Treatment of mild/moderate bleeding episodes in the study with LR769 of a given dose will be regarded as successful if it is concluded that the true percentage of successfully treated bleeding episodes with that dose is greater than 0.55. The primary endpoint for the FDA was established to satisfy the requirements of the US FDA for the evaluation of success.

For primary efficacy endpoint for the EMA, the proportion of bleeding episodes (mild/moderate and severe combined) evaluated with a "good" or "excellent" response at 12 hours after first administration of the study drug will be calculated. This proportion of

success will be evaluated by the European Medicines Agency (EMA) as part of the assessment of the benefit:risk ratio for each dosing regimen.

In addition, the proportions of successfully treated mild/moderate bleeding episodes (according to the primary efficacy endpoint definition) will be compared between the two LR769 treatment dose regimens at a 2-sided alpha of 0.05.

The time to assessment of a “good” or “excellent” response of the bleeding episodes (mild/moderate and severe, separately and combined) by the patient/parent will be analyzed at the bleeding episode level using the Kaplan-Meier (K-M) method to estimate the survival distribution for this endpoint for each treatment regimen separately and combined. Patients who receive rescue medication will be considered failures and will be assigned a censored value of the final timepoint. Patients who do not achieve a “good” or “excellent” response will be censored at the time of last response.

For each treatment, the patient-level mean number of administrations and patient-level mean total amount of drug required per bleeding episode (mild/moderate and severe, separately and combined) will be summarized using descriptive statistics, and a 95% CI for the true mean (across patients) will be calculated based on normal approximation.

*Safety evaluations:*

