### 3.1.2.2 Treatment of Mild/Moderate Bleeding Episodes

Treatment of a mild/moderate bleeding episode will be initiated as soon as possible but certainly within 4 hours of first symptoms of the bleeding episode. Treatment will consist of

an IV administration of either 75 µg/kg or 225 µg/kg of LR769 as a bolus injection administered in  $\leq$  2 minutes.

During the 75 µg/kg treatment regimen, the initial 75 µg/kg dose may be followed 3 hours later with 75 µg/kg every 3 hours until the bleeding is successfully treated. A maximum of 8 treatments in total are allowed in this treatment regimen for mild/moderate bleeding episodes.

During the 225 µg/kg treatment regimen, the initial 225 µg/kg treatment may be followed 9 hours later with 75 µg/kg every 3 hours until the bleeding episode is successfully treated. A maximum of 6 treatments in total are allowed in this treatment regimen for mild/moderate bleeding episodes.

If the bleeding episode is not successfully treated as assessed as an excellent or good response at 24 hours after the first administration, treatment with LR769 may not be continued and alternative treatment must be considered depending on the remaining symptoms (and be noted as concomitant medication). Treatment of this bleeding episode should not be continued with LR769 (study drug) in that case. The patient's physician may determine the best treatment in that case. This may be another bypassing agent [REDACTED]  
[REDACTED] or other hemostatic treatment.

Patients are allowed to be treated for another bleeding episode in a different anatomical location within 24 hours after initial start of treatment, provided the response to treatment of the initial bleeding episode was either "good" or "excellent". Occurrence of a bleeding episode in the same joint/anatomical location after 24 hours of the last treatment of the initial bleeding episode when an initial "good" or "excellent" response has been achieved will be treated as a new bleeding episode. If the bleeding episode occurs within 24 hours after the last treatment of the initial bleeding episode when an initial "good" or "excellent" response has been achieved, this is regarded a true recurrence and therefore a treatment failure. There is no restriction on the number of bleeding episodes that can be treated with LR769 for each patient in this study. The use of LR769 for prophylaxis is not permitted.

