## 9.6 Secondary Endpoints

The secondary efficacy endpoints consist of the following:

- Proportion of mild/moderate bleeding episodes successfully treated according to the same criteria as the primary endpoint of efficacy, at all other timepoints

- Proportion of bleeding episodes (mild/moderate and severe, separately and combined) with a “good” or “excellent” patient (and/or physician when available) reported assessment of efficacy at all timepoints
- Time to assessment of a “good” or “excellent” response of the bleeding episodes (mild/moderate and severe, separately and combined) by the patient (and/or physician when available)
- Descriptive analysis of the number of administrations and mean total amount of drug administered per bleeding episode

For each treatment regimen and both treatment regimens together, the proportions of bleeding episodes successfully treated, according to the same criteria as the primary endpoint of efficacy at all timepoints will be summarized using descriptive statistics, and a 95% CI for the true mean patient level proportion will be calculated based on normal approximation.

For each treatment regimen and both treatment regimens together, the proportions of bleeding episodes with a “good” or “excellent” patient reported assessment of the efficacy at all timepoints will be summarized using descriptive statistics, and a 95% CI for the true proportion will be calculated based on normal approximation.

The time to assessment of a “good” or “excellent” response of the bleeding episodes (mild/moderate and severe, separately and combined) by the patient/parent will be analyzed at the bleeding episode level using the K-M method to estimate the survival distribution for this endpoint for each treatment regimen separately and combined. Patients who receive rescue treatment at any time will be considered failures and will be assigned a censored value at the final timepoint. Patients who do not achieve a “good” or “excellent” response will be censored at the time of last response.

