- Proportion of bleeding episodes (mild/moderate and severe, analyzed separately and combined) with a “good” or “excellent” patient (and/or physician when available) reported assessment of efficacy
- Proportion of bleeding episodes still ongoing

The time reported on the plots defined above will be derived as a difference between the time of event (success or end of the bleeding episode) and the time of first study drug injection for the associated bleeding episode.

Additionally, a new analysis summarizing the number of injections required to produce a response (FDA and EMA definition analyzed separately) and time required to reach a response will be conducted. This analysis will also be re-run stratifying by age group using the same thresholds as discussed above. Mock Tables for this analysis can be found in section 3. Time required to reach a response will also be analyzed using the Kaplan-Meier model, as described in the main SAP.

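### In the combined mild/moderate-plus-severe time-to-response analysis, known mild/moderate failures are censored at 24 h or at an undefined final timepoint, so the Kaplan-Meier curve after 24 h can rise above the true response share

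*Protocol*

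**What the plan says.** Protocol Section 9.6 says that time to a good or excellent rating "will be analyzed at the bleeding episode level using the K-M method to estimate the survival distribution for this endpoint", for each regimen and both together, and for mild/moderate and severe bleeds separately and combined. Two censoring rules follow.

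- Rescue: "Patients who receive rescue treatment at any time will be considered failures and will be assigned a censored value at the final timepoint". The synopsis (Statistical Methods) has the same rule: such cases "will be assigned a censored value of the final timepoint". Neither place defines the final timepoint.
- No response: those without a good or excellent "response will be censored at the time of last response".

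A bleed that is rescued and never responds meets both rules, and no precedence is given.

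Follow-up differs by severity. For mild/moderate bleeds the synopsis (Duration of Treatment) sets the last dose at 21 hours, "with an efficacy assessment at 24 hours after initiation of treatment". If there is no good or excellent rating by then, "treatment with LR769 may not be continued and alternative treatment must be considered". Severe bleeds may be treated for several days. Appendix 1 (severe bleeding schedule, footnote 3) has them rated every 12 hours if treatment goes beyond 24 h, and again 12 hours after the last dose.

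The SAP addendum (Section 2) repeats the combined time-to-response analysis by age group and BMI tertile. Its Section 3 shells give Kaplan-Meier quartiles for bleeds regardless of severity, overall and in three age strata. On method it says: "Time required to reach a response will also be analyzed using the Kaplan-Meier model, as described in the main SAP". The main SAP is not among the documents.

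**The concern.** Kaplan-Meier treats a censored bleed as one that could still respond, at the rate seen in the bleeds left at risk. That is reasonable for a bleed whose later ratings are missing. It is not reasonable for a mild/moderate bleed rated none or moderate at 24 h: its treatment with study drug is over and its outcome is known.

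In a mild/moderate-only curve this does no harm, because nothing happens after 24 h. In the combined curve, only severe bleeds can remain at risk once the mild/moderate failures have been censored. Each late severe response then moves the whole curve, including the part that stands for those failures. At stake are the response share shown after 24 h and any quartile read there.

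**Working it through.** **The plan's own figures.** The documents give no figure for this analysis. The only related figure is the power of at least 80% for the primary test (Section 9.2), and it reproduces. The design effect is 1 + (8 − 1) × 0.1 = 1.7, so the effective n is 176/1.7 = 103.5 per regimen. Power is 81.5% with the null standard error and 86.2% with the alternative one. The present point does not touch it.

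**Inputs.** From the documents: 352 mild/moderate bleeds, and a last mild/moderate rating at 24 h. Assumed: 30% mild/moderate failures (0.30 × 352 ≈ 106); 10 severe bleeds, of which 7 respond by 24 h and 3 are unresolved; late severe responses at 36, 48 and 60 h. The 30% is illustrative. The plan's 0.70 success rate refers to the stricter 12 h endpoint, not to good or excellent ratings by 24 h. The protocol calls severe bleeds a minority (Section 9.5.1) but gives no number.

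**Curve at 24 h.** Responders are 246 + 7 = 253 of 362, so S(24) = 109/362 = 0.3011 and the response share is 69.9%. This is exact.

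**Curve after 24 h.** S(end) = 0.3011 × Π(1 − 1/r), where r is the number at risk at each late response. If all 106 failures leave at 24 h, r starts at 3. If h failures are held to the end of the axis, r starts at h + 3.

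| Failures held (h) | Late severe responders | True share | Curve ends at | Q3 |
|---|---|---|---|---|
| 0 | 3 of 3 | 256/362 = 70.7% | 1 − 0.3011 × (2/3)(1/2)(0) = 100% | 36 h |
| 0 | 2 of 3 | 255/362 = 70.4% | 1 − 0.3011 × (2/3)(1/2) = 90.0% | 36 h |
| 0 | 1 of 3 | 254/362 = 70.2% | 1 − 0.3011 × (2/3) = 79.9% | 36 h |
| 0 | 0 of 3 | 253/362 = 69.9% | 69.9% | not reached |
| 26 (a quarter) | 3 of 3 | 70.7% | 1 − 0.3011 × 26/29 = 73.0% | not reached |
| 53 (half) | 3 of 3 | 70.7% | 1 − 0.3011 × 53/56 = 71.5% | not reached |
| 106 (all) | 3 of 3 | 70.7% | 1 − 0.3011 × 106/109 = 70.7% | not reached |

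In the first three rows Q3 is reported as 36 h, although fewer than 75% of bleeds ever responded. If no severe bleed is unresolved at 24 h, there is no inflation.

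**Other failure shares** (h = 0, all 3 late severe bleeds respond). With 10%, 50% and 70% mild/moderate failures, the true shares are 327/362 = 90.3%, 186/362 = 51.4% and 116/362 = 32.0%; the curve ends at 100% each time. At 10% the median and Q3 do not change.

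**One regimen.** Take 22 × 8 = 176 mild/moderate bleeds, 53 of them failures, and 5 severe bleeds of which one first responds after 24 h. The true share is (123 + 5)/181 = 70.7%. That one bleed is alone in the risk set, so its response takes the curve to 100%.

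**The case against.** The strongest objection is the rescue rule. Section 7.2.1 (24-hour procedures) and the rescue sections (3.1.2.4 and 7.2.3) direct that a bleed without sufficient effect at 24 h be given other treatment, so most mild/moderate failures may count as rescued. If the final timepoint is the end of the axis, those bleeds are handled correctly. Even a quarter of failures held there brings the example down to 73.0%. This stands as a limit on size. It does not settle the point: the term could equally mean the bleed's own 24 h rating. Section 3.1.2.2 also says only that "alternative treatment must be considered depending on the remaining symptoms", so failures without rescue can occur.

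A reader might infer that the combined curve runs to nearly 100% whatever share of bleeds failed. The documents do not support that. It requires failures to have left the risk set at 24 h, at least one severe bleed unresolved then, and the last bleed at risk to respond. Days of treatment do not show late response, because the event is the first good or excellent rating and severe bleeds continue to be dosed after it. Late first responses are still foreseen: for severe bleeds in the 75 µg/kg regimen, Section 7.2.2.3 describes 3-hourly dosing over 1–2 days until such a rating is reached.

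Nor are the failures hidden. Mild/moderate bleeds have their own curve, proportions at each timepoint and the share needing alternative treatment are reported, and the addendum shell prints event and censored counts beside the quartiles.

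Finally, the main SAP may define the final timepoint and the time horizon. If so, that part needs only alignment. A definition alone would not change the protocol's separate rule for non-responders without rescue.

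**Conclusion.** The point holds in a limited form. For unrescued mild/moderate failures the stated rule is wrong in the combined curve after 24 h; for rescued failures the rule is undefined. If any severe bleed first responds after 24 h, the curve can exceed the true response share, and it reaches 100% when the last bleed at risk responds and the failures have already been censored. In the example the excess runs from about 10 percentage points (79.9% against 70.2%) to about 29 (100% against 70.7%). It is 0.8 to 2.3 points if a half to a quarter of failures are held to the end, and zero if all are held or no late severe response occurs. These sizes rest on assumed severe-bleed counts and an illustrative failure share.

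Estimates up to 24 h, the separate mild/moderate curve and the primary endpoint with its test and power are unaffected. For the curves, this assumes that failures stay in the risk set until the mandatory 24 h rating. Q3 is affected only where response by 24 h is below about 75%, which can also happen by chance in the small addendum strata. This is a minor correction to a secondary estimate with no planned test.

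**What to change.** In Section 9.6, the synopsis, the main SAP and the addendum:

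- Define the final timepoint as the longest time on the curve being estimated.
- Apply it to every known failure: rescued, or not good or excellent at the 24 h or last scheduled rating. State that this rule takes precedence.
- Keep censoring at the last rating only for bleeds whose later scheduled ratings are missing.

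Reporting the cumulative incidence of response with failure as a competing event gives the same curve when no ratings are missing. Alternatively, end the combined curve at 24 h and keep rescued bleeds in the risk set to that point.

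The cost is one sentence in each document and one line in the derivation of the censoring time. The downside is that the reported response share after 24 h may look less favourable.

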## 9.7 Tertiary Efficacy Endpoints

The tertiary efficacy endpoints consist of the following:

- Proportion of bleeding episodes (mild/moderate and severe, separately and combined) with a “good” or “excellent” physician reported assessment of the efficacy at 12 hours (if available)
- Proportion of recurrences (defined as a bleeding in the same joint/anatomical location within 24 hours after an initial successful response)
- Proportion of bleeding episodes (mild/moderate and severe, separately and combined) requiring alternative treatment
- Proportion of bleeding episodes (mild/moderate and severe, separately and combined) with successful pain relief

For each treatment, the mean number of administrations and mean total amount of drug administered per bleeding episode (mild/moderate and severe, separately and combined) will

be summarized using descriptive statistics. Also a 95% CI for the true mean will be calculated based on normal approximation.

## **9.8 Safety Analyses**

All AEs will be coded using MedDRA. The number and percentage of patients with any AEs, any SAEs, and any TEAEs will be presented for all patients and for the different dose regimens and Phases A and B separately. An AE will be considered treatment related if it has a definite, probable, or possible relationship to the study treatment or if the relationship to the study treatment is missing. AEs will be summarized at the patient level by MedDRA SOC and PT using frequencies and percentages. AEs will also be tabulated at the event level by SOC, PT, and severity and by SOC, PT, and relationship to study treatment.

Descriptive statistics for the actual value at each timepoint and the change from baseline to each post-baseline timepoint in systolic and diastolic BP, heart rate, respiratory rate, and body temperature will be tabulated for each treatment. Two-sided paired t-tests will be used to test whether the mean changes from baseline equal 0. Baseline is defined as the last measurement prior to study treatment.

For continuous laboratory parameters, descriptive statistics for the actual value at each timepoint and the change from baseline (screening) to each post baseline timepoint will be tabulated for each treatment. Two-sided paired t-tests will be used to test whether the mean changes from baseline equal 0. Shift tables for laboratory parameters will be prepared.

## **9.9 Pharmacokinetic Analyses**

A separate PKAP will be written and signed off prior to performing the analyses.

Descriptive statistics for plasma concentrations at each timepoint and for PK parameters will be tabulated and FVIIa concentration data (as measured by activity assay) over time will be graphically presented.

Pharmacokinetic data analysis will be performed using non-linear mixed effects modeling, which considers the repeated PK observations as a function of time using all available PK data collected in hemophilia patients who have received LR769 to date. Estimates and summary statistics of PK parameters (clearance,  $C_l$ ; volume of distribution,  $V_d$ ; terminal half-life,  $t_{1/2}$ ; area under the plasma concentration-time curve from time 0 to infinity,  $AUC_{0-\infty}$ ; and maximum plasma concentration,  $C_{max}$ ) will be presented by dose group. The analyses will closely follow the guidelines of the US FDA and EMA for performing and reporting population PK analyses (FDA, 1999; EMA, 2007).

Analyses of the PK of LR769 in pediatric patients will be based on the evaluable PK population. It is expected that at least 10 of the 12 PK patients in each age group will be evaluable (for both PK assessments).

